4.3.2 Per Protocol Dataset

The Per Protocol Analysis Set (PPAS) will consist of all subjects included in the FAS who have measurements on all primary and secondary variables on all three periods and have no major protocol violations.

4.4 Additional Statistical Considerations

4.4.1 Missing, Unused or Spurious Data

No imputation of missing data will be performed, i.e. an observed case approach will be used in the statistical analyses.

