7.3.3 Adaptive Speech recognition in noise (Matrix test)

The purpose of this test is to establish the test subject's ability to recognise speech in the presence of background noise. The adaptive speech test in noise shall be conducted using validated lists of phonetically balanced sentences, with speech presented in sound-field from the front (0 degrees azimuth) and noise will also be presented from the front (figure 4). The noise shall be kept constant at 65 dB SPL, and the speech shall be adapted stepwise according to the software used to establish the speech-to-noise ratio (SNR) providing a 50% level of understanding.

Software and speech material to be used is the Matrix test in language specific versions as applicable.

The test shall be performed with the non-test ear blocked (in case of normal or near-normal hearing or a large asymmetry with the non-test ear having significantly better hearing thresholds).

The speakers should be at the height of the test subjects head and more than 1 metre away from the test subject. There should preferably be more than 1 metre of free space around the test subject in all directions. This is in accordance with the current standard.

FRONT

Figure 5: Speech in noise speaker position

At Visit 1 and 2, the speech in noise test will be performed for the aided situation with Baha 6 Max SP or Baha 5 SP depending on the randomisation order.

At visit 3 the test will be performed unaided.

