7.3.4 Sound-field threshold

The purpose of this test is to establish the hearing thresholds in sound-field [0.25, 0.5, 1.0, 2.0, 3.0, 4.0, 6.0, 8.0 9.0 and 10.0 kHz] through a speaker in front position (0 degrees azimuth) according to the so-called ascending or modified Hughson-Westlake method (Figure 10). The test shall be performed with the non-test ear blocked (in case of normal or near-normal hearing or a large asymmetry with the non-test ear having significantly better hearing thresholds). The signal to be used should be warble tones.

At Visit 1 and 2, the sound-field thresholds will be measured in the aided situation with Baha 6 Max SP or Baha 5 SP depending on the randomisation order.

At visit 3 the test will be performed unaided.

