The distribution of continuous variables will be given as mean, standard deviation, median, Q1, Q3, minimum and maximum and of categorical variables as numbers and percentages.

If a subject completes the cross over part but not the final visit, he will be included in the comparison between Baha 6 Max SP and Baha 5 SP but not in the comparison Baha 6 Max SP vs unaided in FAS.

The investigation will be completed when there are as many available subjects that are needed in the primary analyses.

The main analyses will be on the full analysis set (FAS) and complementary analyses on the Per protocol population. No imputation of missing data will be performed.

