9.4 Sample Size Determination

First primary analysis: Baha 6 Max SP vs unaided regard Adaptive speech in noise

Assuming an individual mean difference (aided Baha 6 Max SP minus unaided) in speech recognition in noise of 16 dB SNR with a standard deviation (SD) of 12.5 (Busch et al, 2015), a total sample of 15 eligible subjects are required to provide 90% power to reject the null hypothesis for the statistical test for the primary objective (change in dB SNR) using a two sided, alpha 0.005, with Two-sided Fisher's non-parametric permutation test for paired observations. As this is an internal Cochlear investigation, patients will be recruited until the number of required patients are obtained. Hence, no dropouts are expected (8).

Second primary analysis: Baha 6 Max SP vs Baha 5 SP regarding preference of device.

Assuming that 86% prefer Baha 6 Max SP, then 16 subjects are needed for 80% power with two-sided Sign test on significance level 0.045.

In order to satisfy both sample sizes for the primary analyses 16 subjects will be randomised into the investigation.

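### Neither document says how to score an attempted test that cannot be measured at the equipment limit, while both bar imputation and the SAP analyses observed cases only

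*SAP*

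**What the plan says.** On missing data, SAP 4.4.1 reads "No imputation of missing data will be performed, i.e. an observed case approach will be used in the statistical analyses". Protocol 9.1 says "No imputation of missing data will be performed". The protocol adds one specific case: a subject who completes the crossover but not the final visit stays in the device comparison "but not in the comparison Baha 6 Max SP vs unaided in FAS".

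On the speech test, Protocol 7.3.3 says "The noise shall be kept constant at 65 dB SPL, and the speech shall be adapted stepwise according to the software used", with 50% understanding as the target. It gives no highest speech level, no stopping rule, and no score for a run that fails to converge. The unaided condition is measured only at Visit 3.

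On thresholds, Protocol 7.3.4 lists "0.25, 0.5, 1.0, 2.0, 3.0, 4.0, 6.0, 8.0 9.0 and 10.0 kHz] through a speaker in front position". It gives no code for a tone that gets no response.

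The first primary in Protocol 9.3.1 and 9.6 is the paired comparison of Baha 6 Max with unaided hearing, tested at 0.005. Protocol 9.6 allows a 5% retest if the other primary succeeds. SAP 4.2.2 instead describes the first primary as a comparison of responders between Baha 6 Max and Baha 5, although SAP 4.1 still sizes the trial on the unaided comparison. The per-protocol sets (Protocol 9.5.2, SAP 4.3.2) require every primary and secondary measurement in all three periods.

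**The concern.** Subjects have conductive or mixed hearing loss. They are tested unaided, with the other ear blocked where it is near-normal or much better. A loudspeaker has a highest level, so some unaided runs may never reach 50% and some high-frequency tones may get no response. Such a result is not unknown. It is known to be worse than the limit, so it is censored.

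The plan has no rule that gives this result a number. Beside an observed-case rule, an empty field is easily read as missing, and the pair then drops out. The loss depends on the outcome: in the unaided comparison it falls on the subjects with the most to gain, so the estimated benefit shrinks and power falls. There is little reserve, since 15 pairs are needed, 16 are planned, and no dropout is allowed for.

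The per-protocol set is more exposed, because one unanswered tone at one frequency can remove the subject from it altogether.

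**Working it through.** **Step 1: the plan's own figure.** Protocol 9.4 gives a difference of 16 dB, "with a standard deviation (SD) of 12.5", two-sided alpha 0.005, and states that "a total sample of 15 eligible subjects are required to provide 90% power". The standardised difference is 16/12.5 = 1.28. Paired t power from the noncentral t is 89.2% at n = 14, 92.4% at n = 15 and 94.7% at n = 16. Simulation of the paired permutation test gives about 88% at 14 and 92% at 15. The stated 15 is reproduced.

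**Step 2: assumptions not in the documents.** The 16 dB is taken as the size of the benefit. Aided SNR is assumed to have mean 0 dB and SD 2, independent of the benefit. Unaided SNR = aided SNR + benefit, so its mean is 16 and its SD is √(12.5² + 2²) = 12.66. The limit L is varied from +20 to +40 dB SNR. With noise at 65 dB SPL, that is speech at 85 to 105 dB SPL.

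**Step 3: pairs lost and mean of those left.** Let a = (L − 16)/12.66, with φ and Φ the standard normal density and distribution function.

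- Expected pairs lost = 16 × [1 − Φ(a)].
- Mean benefit among remaining pairs = 16 − (12.5²/12.66) × φ(a)/Φ(a).

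Example, L = 20: a = 0.316 and Φ(a) = 0.624. Lost = 16 × 0.376 = 6.0. Mean = 16 − 12.34 × 0.608 = 8.5 dB.

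**Step 4: power.** This was simulated with a paired t-test, n = 16. The Holm column needs the power of the preference test. At n = 16 the sign test rejects with 13 or more preferences for one device (two-sided p = 0.0213), so power at the plan's 86% is 82.4%. With independent endpoints, Holm power = 0.824 × (power at 0.05) + 0.176 × (power at 0.005). For L = 20 this is 0.824 × 0.757 + 0.176 × 0.423 = 0.698.

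| Limit (dB SNR) | Pairs lost of 16 | Mean benefit, pairs dropped | Power at 0.005 | Power at 0.05 | Power with Holm retest | Mean benefit, limit value kept | Power at 0.005, limit value kept |
|---|---|---|---|---|---|---|---|
| +20 | 6.0 | 8.5 dB | 42% | 76% | 70% | 12.7 dB | 95% |
| +25 | 3.8 | 11.0 dB | 68% | 93% | 88% | 14.2 dB | 96% |
| +30 | 2.2 | 12.9 dB | 84% | 98% | 95% | 15.1 dB | 96% |
| +40 | 0.5 | 15.2 dB | 93% | 99.6% | 98% | 15.9 dB | 95% |

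**Step 5: a check without an assumed limit.** Suppose the k largest of 16 benefits are the unmeasurable ones, and use the permutation test at 0.005. Dropping two gives about 13.3 dB and 78–84% power. Dropping four gives about 11.0 dB and 60%. Dropping six gives about 8.8 dB and 30%. Keeping them at the largest measured benefit holds power at about 92–94%. Simulation error is about 1 to 3 points.

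**Step 6: per-protocol set, illustration only.** Ten frequencies in three conditions make 30 threshold values per subject. If each had an independent 1% chance of no response, 16 × 0.99³⁰ = 11.8 subjects would remain; at 2%, 16 × 0.98³⁰ = 8.7. Protocol section 6 lists only eight frequencies for the unaided comparison, which would ease this slightly.

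**The case against.** The strongest reply is that dropping is nowhere written. A reader might infer that the plan orders the removal of unmeasurable results. It does not: the rules concern missing data, and a site could record the limit value without breaking them. The protocol leaves the adaptation to the Matrix software, and the documents do not say what that software returns at its ceiling. This stands. The defect is an absent scoring rule.

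A reader might also infer that SAP 4.4.1 strips unaided evidence from the SAP's first primary. It cannot. SAP 4.2.2, 4.2.3 and 4.3.1 name only the two devices, so the harm applies to the protocol's first primary and its unaided secondaries. The gap still touches the SAP: its responder rule in 4.2.1 does not say whether a subject who never reaches 50% is a non-responder or missing.

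A third tempting reading is that the device threshold comparison is pulled toward no difference. The documents do not support a direction. Dropping pairs in which one device gets no response loses information, but the bias depends on which device that is.

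On size, the limits and the aided mean are assumptions. Inclusion is restricted to conductive or mild to moderate mixed loss, so frequent unaided failure is not established. Whether the assumed 16 dB already includes ceiling scores cannot be checked. The Holm retest recovers much of the power, and only the two lowest limits then fall below 90%. Protocol 9.1 and 9.4 also speak of recruiting until enough subjects are available, so a shortfall below 15 pairs is not certain, although 7.2.6 bars replacing withdrawn subjects. These points narrow the power argument. Neither the retest nor extra recruitment removes the outcome-dependent selection, which still shrinks the estimate.

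**Conclusion.** The point holds as a gap: attempted but unmeasurable results have no score, and both documents bar imputation. If such results are entered as blanks, the protocol's estimate of benefit over unaided hearing is biased downward, and the per-protocol set can lose subjects over a single tone.

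The size is a range that rests on the assumed limit, the assumed aided distribution and normal differences. At a limit of +40 dB the effect is small. At +20 dB the mean benefit roughly halves and power at 0.005 falls below 50%. The Holm figures further assume that preference and speech in noise are independent and that 86% prefer Baha 6 Max. Scoring at the limit keeps power near 95% at 0.005 in every case examined, with a mean of 12.7 to 15.9 dB.

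A reader might take any limit-scored mean as a lower bound. That is right only where the unaided value alone is at the limit. If a Baha 6 Max value is at the limit, the score flatters that device.

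**What to change.** Before database lock, amend Protocol 9.1 and SAP 4.4.1 as follows.

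- State that a test attempted but not measurable at the highest available level is not missing data. Name that level for the Matrix test and for each tone frequency.
- Record it with its own eCRF code, score it at the limit, keep the subject in the full analysis set comparisons, and count it as a measurement for the per-protocol set.
- Report the number of such values per condition. Add a sign test on the direction of the paired difference as a sensitivity analysis.
- Call the mean difference conservative (a lower bound) only where the unaided value alone is at the limit.
- Keep the no-imputation rule for tests that were not performed.

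The SAP's first primary (4.2.1 and 4.2.2, Baha 6 Max against Baha 5) must also be reconciled with the protocol's comparison against unaided hearing. Otherwise the rule has no agreed analysis to apply to.

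The cost is a few sentences and one eCRF code. The downside is that the reported mean benefit is conservative when unaided values lie at the limit.

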4.4.2 Planned Interim Analysis

Not applicable.

4.4.3 Criteria for Termination of the Clinical Investigation

Not applicable.

4.4.4 Additional Statistical Analyses

No additional analysis will be conducted.

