9 STATISTICAL CONSIDERATIONS

9.1 General Statistical Considerations

The investigation will have two primary analyses, one regarding Adaptive speech in noise between Baha 6 Max SP and unaided hearing ($\alpha = 0.005$) and one regarding preference between Baha 6 Max SP and Baha 5 SP ($\alpha = 0.045$). These endpoints will be evaluated using the decision rules of the Holm's test. (Ref NEJM2). With these procedures we will have a total type I error <0.05 .

For the comparison between the Baha 6 Max SP and unaided the design don't take care of period effect so the statistical analyses will be paired. For the comparison between Baha 6 Max SP and Baha 5 SP a cross over design was applied and the statistical analyses will be adjusted for period effect.

The main results for all outcome variables are the estimate of mean differences with 95% confidence interval (CI) with a descriptive p-value. The p-value will only have a confirmatory value for the two primary analyses.

For comparison between the Baha 6 Max SP and unaided Fisher's non-parametric permutation test for paired observations will be used for continuous variables and Sign test for dichotomous variables and ordered categorical variables.

For the comparison between Baha 6 Max SP and Baha 5 SP the following period adjusted analysis should be performed for continuous variables: For each subject take the difference between the measurement in second period and the measurement in first period. Then analyse these differences between the subjects randomised to Baha 6 Max SP in the first period and the subjects randomised to Baha 5 SP in the first period with Fisher's two-sided non-parametric permutation test. The Fisher's permutation test is preferable because it is non-parametric and gives consistent 95% CI.

For the comparison between Baha 6 Max SP and Baha 5 SP the following period adjusted analysis should be performed for dichotomous and ordered categorical variables: For each subject take the difference as, improved no change and worsened, between the measurement in second period and the measurement in first period. Then analyse these ordered categorical differences between the subjects randomised to Baha 6 Max SP in the first period and the subjects randomised to Baha 5 SP in the first period with Mantel-Haenszel chi-square test.

For comparison of preference of device between Baha 6 Max SP and Baha 5 SP the Sign test will be used.

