9.6 Primary Endpoint Analyses

The first primary endpoint analysis will be the comparison of adaptive speech in noise [signal-to-noise ratio, 50% speech understanding] between the Baha 6 Max SP and unaided with two-sided Fisher's non-parametric permutation test for paired observations on significance level 0.005 on the FAS population. Mean difference with 99.5% confidence interval will be given together with the distribution of the difference.

The second primary endpoint analysis will be the comparison between Baha 6 Max SP and Baha 5 SP regarding preference of device with two-sided Sign test on significance level. Proportion of preferences for Baha 6 Max SP with exact 95 % CI will be calculated.

If one of the two primary efficacy analyses are significant but not the other, the other can be retested at the 5% significance level according to the decision rule of the Holms test (9).

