4.2.3 Secondary Hypotheses

For continuous variables and ordered categorical variables the Wilcoxon signed rank test will be applied and for binary variables the Binomial test will be applied when testing the null-hypothesis that the Baha 6 Max SP and the Baha 5 SP are equal.

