4.7 Presentation of Data

Listing of all subject data will be done and presented in the statistical report.

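### The SAP plans tests and listings but none of the estimates, confidence intervals or summaries that the protocol makes its main results, and SAP 4.4.4 read literally excludes them

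*SAP*

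**What the plan says.** Protocol 9.1 sets the reporting standard: "The main results for all outcome variables are the estimate of mean differences with 95% confidence interval (CI) with a descriptive p-value". It limits the role of testing: "The p-value will only have a confirmatory value for the two primary analyses". It also gives the interval as a reason for choosing the test: "The Fisher's permutation test is preferable because it is non-parametric and gives consistent 95% CI". The same section requires means, SDs, medians, quartiles and ranges for continuous variables, and counts with percentages for categorical ones.

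Protocol 9.6 adds outputs for the two primary analyses. For speech in noise, Baha 6 Max against unaided: "Mean difference with 99.5% confidence interval will be given together with the distribution of the difference". For preference: "Proportion of preferences for Baha 6 Max SP with exact 95 % CI will be calculated".

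SAP section 1 calls the document a companion to the protocol, claims to cover both the analyses and their presentation in full, and says that deviations from it will be reported. Its analysis content is as follows:

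- 4.2.1: a two-sided p-value below 5% counts as success.
- 4.2.2: a Binomial test for each primary. The first compares responder proportions between Baha 6 Max and Baha 5.
- 4.2.3: "For continuous variables and ordered categorical variables the Wilcoxon signed rank test will be applied", with a Binomial test for binary variables, again for Baha 6 Max against Baha 5 only.
- 4.4.4: "No additional analysis will be conducted".
- 4.7: "Listing of all subject data will be done and presented in the statistical report".

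**The concern.** A report that followed the SAP and nothing else would contain p-values and listings. The study is described as pivotal and is meant to support regulatory approval with 16 subjects. A p-value does not show how large the gain over unaided hearing is, or how large a deficit against Baha 5 is still compatible with the data. For the secondary outcomes, whose p-values the protocol treats as descriptive, the estimate and interval are the result.

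This is more than missing detail. The SAP replaces a test that the protocol chose partly for its interval with tests that do not give a mean difference. It also leaves out the unaided comparison to which the 99.5% interval belongs.

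**Working it through.** **Step 1. Required outputs against planned outputs.**

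| Output | Protocol | SAP |
|---|---|---|
| Speech in noise, Baha 6 Max vs unaided | Paired permutation test, mean difference, 99.5% CI (9.6) | No such comparison; Binomial test of responders vs Baha 5 (4.2.2) |
| Preference | Sign test, proportion, exact 95% CI (9.6) | Binomial test only (4.2.2) |
| Continuous secondaries vs Baha 5 | Period-adjusted permutation test, mean difference, 95% CI (9.1) | Wilcoxon signed rank test only (4.2.3) |
| Continuous secondaries vs unaided | Paired permutation test, mean difference, 95% CI (9.1) | None |
| Descriptive summaries | Required (9.1) | Listings only (4.7) |

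Inverting a Wilcoxon signed rank test gives an interval for a pseudo-median, and inverting a Binomial test gives one for a proportion. The SAP asks for neither, and neither is a mean difference. The Wilcoxon test on paired device differences also has no period adjustment. The SAP is based on protocol version 3.0, and the change history shows that version 4.0 altered only section 8.4, so this is not a version gap.

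**Step 2. The protocol's own figures (9.4).**

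- First primary: difference 16 dB, SD 12.5, two-sided alpha 0.005, n = 15. The noncentrality is (16/12.5) × √15 = 4.96. Paired t-test power is 92.4% at n = 15 and 89.2% at n = 14. A simulated sign-flip permutation test gives about 91.6% and 87.7%. Fifteen is the smallest n that reaches 90%.
- Second primary: 86% preference, two-sided alpha 0.045, n = 16. At least 13 preferences are needed, since 2 × (560 + 120 + 16 + 1)/65,536 = 0.0213. Power is 82.4%, above the stated 80%.

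The stated sample sizes hold, and the point does not depend on them.

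**Step 3. What the missing intervals would show at n = 16.**

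- First primary, with a t-based interval standing in for the permutation interval: half-width = t(15 df) × 12.5/√16.
  - 99.5%: 3.286 × 3.125 = 10.3 dB, so an observed 16 dB gives 5.7 to 26.3 dB.
  - 95%: 2.131 × 3.125 = 6.7 dB, giving 9.3 to 22.7 dB.
- Preference, if all 16 subjects state one (Clopper-Pearson 95%):
  - 13/16: p = 0.021, interval 0.54 to 0.96.
  - 12/16: p = 0.077, interval 0.48 to 0.93.
- Baha 6 Max vs Baha 5, continuous outcomes in dB: the documents give no SD. Assuming a paired SD of 1 to 5 dB, the simple paired 95% half-width is 2.131 × SD/4, or 0.5 to 2.7 dB. This ignores the period adjustment.

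**Step 4. Interval level and the Holm rule.** Protocol 9.6 lets one primary be retested at 5% if the other is significant. If speech in noise is retested, the 99.5% interval no longer matches the decision and a 95% interval is needed beside it. For preference with 16 stated preferences, the critical count is 13 at both 0.045 and 0.05, so the exact 95% interval serves either way.

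**The case against.** The strongest reply is that the SAP is a companion to the protocol and revokes nothing in section 9. Its sample-size text draws openly on the protocol. It is equally silent on the safety and demographic summaries of protocol 9.8 and 9.9, and nobody would take those as cancelled. Section 4.4.4 sits among entries marked not applicable in a document that was fitted into a sponsor template, and may mean only that nothing is added to what is already planned. The listings would also let anyone recompute every estimate for 16 subjects, and for preference the count is itself the effect size.

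Much of this stands. A reader might infer that the estimates and intervals will never be produced, or that they are lost. The documents do not support that: they show only that the SAP does not plan them and that 4.4.4, taken literally, leaves no room for them.

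The reply does not remove the conflict. The SAP claims full coverage and says that departures from it will be reported, so on a literal reading the protocol's main results would themselves be deviations. Because the SAP changes the tests and the first primary comparison, its silence cannot safely be read as adopting section 9. Being able to recompute from listings is not a plan.

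Two limits on the preference example are fair. Different verdicts on either side of a threshold are common to all discrete tests. The example also assumes that every subject states a preference, whereas protocol 9.3.1 conditions on those who do.

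**Conclusion.** The point holds as an unresolved conflict between the documents. The SAP plans no effect estimate, confidence interval or summary statistic, while protocol 9.1 and 9.6 make estimates with intervals the main results. It affects both primaries and all secondaries. It is most serious for Baha 6 Max against unaided hearing, where the SAP has no comparison to which an interval could be attached, and least serious for preference, where the exact interval follows from the count. It does not in itself bias an estimate or change an error rate.

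The interval widths are illustrations. They rest on the protocol's SD of 12.5 for the unaided comparison, on 16 stated preferences, and on an assumed SD range for the device comparison. The conflict rests on the text alone.

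**What to change.** 1. SAP 4.2.2, first primary: restore the SNR comparison of Baha 6 Max with unaided hearing, using the paired permutation test and the mean difference with its 99.5% interval. Add a 95% interval if this endpoint is retested at 5% under the Holm rule.
2. SAP 4.2.2, second primary: report the proportion preferring Baha 6 Max among those stating a preference, with its exact 95% interval.
3. SAP 4.2.3: for continuous outcomes against Baha 5, use the period-adjusted permutation test of protocol 9.1 with the mean difference and 95% interval. For continuous secondaries against unaided hearing, use the paired permutation test with the mean difference and 95% interval.
4. SAP 4.7: add the descriptive summaries of protocol 9.1 by condition.
5. SAP 4.4.4: reword to say that there are no analyses beyond protocol section 9 and the SAP.

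The cost is SAP wording and a few output tables. No new data are needed.
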